The proposed study seeks to overcome these obstacles by using a telehealth delivery platform (i.e., video-to-home; "V2H" or "CVT-H") to test the effectiveness of a 10-session cognitive-behavioral treatment (CBT) package, tailored to address the unique needs of Veterans with dPD. Preliminary studies provide strong support for the current trial. **V2H allows Veterans to use their computer's webcam to interact with their providers using videoconferencing, via the VA's secure telehealth connection.**

The current trial builds on several earlier trials that have shown support for this intervention to treat depression in PD.

First, this CBT package was initially tested in a face-to-face RCT with 80 people with dPD (and Care-partners), who were randomized to receive CBT plus standard care or standard care only for 10 weeks. The Hamilton Depression Rating Scale ¹⁴ (HAM-D 17) was the primary outcome. Treatment response was defined a priori as a rating of a 1 or 2 on the Clinical Global Impression-Improvement Scale ¹⁵ (CGI-I; a 7 point scale with scores ranging from 1 [very much improved] to 7 [very much worse]) or ≥50% reduction in the baseline HAM-D 17 score. Patients were evaluated at baseline, midpoint (week 5), endpoint (week 10), and one-month follow-up (week 14). CBT was associated with greater improvements in depression, [HAM-D 17; F(3,215)=30.74 P<.0001; Cohen's d=1.59] & Beck Depression Inventory (BDI) F(3,210)=9.77 P=.001; Cohen's d=1.10], anxiety [F(3,214)=11.65 P=.001; Cohen's d=.98], quality of life [F(3,209)=5.07 P=.02, Cohen's d=.81], coping [F(3,204)=4.25, P=.05; Cohen's d=.80] , and motor disability [F(1,68)=5.9 P=.02; Cohen's d=.13] vs. control. At week 10, 56% patients receiving CBT and 8% receiving standard care were treatment responders, as defined above (Fisher's exact P<.0001). At week 14, 51% of CBT patients and 0% of patients in the standard group met criteria for response (Fisher's exact P <.0001).

Second, this treatment was repeated in an uncontrolled trial, where the intervention was delivered via telephone. Within group CBT effect sizes for telephone delivery showed a similar treatment effect, compared to effect sizes obtained via face-to-face delivery. This telephone-based CBT protocol was provided to 21 patients and Care-partners, resulting in significant improvements in depression [HAM-D

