3.3 Sample Size Justification & Subject Selection

The study will enroll a total of 180 subjects (90 Veterans + 90 of their Care-partners), from VA New Jersey, who have Parkinson's Disease and depression. 1,199 Veterans with dPD were served in VA New Jersey during the last four fiscal years. Several methods of recruitment (see Recruitment and Consent below) will be used to enroll this pool of Veterans.

Our Power Analyses assume 180 participants (90 enrolled dyads) with 144 participants (72 dyads, 36 dyads each arm), completing the study. Observed standard deviations in the power calculations that follow are taken from control group baseline data in [name] et al.¹⁶ For the primary test of treatment differences in HAM-D scores, controlling for baseline HAM-D scores and demographic covariates, the current study is powered to detect a 2.5 point HAM-D treatment difference between groups. For comparison, we observed a group difference of 7.30 in [name] et al.¹⁶ For the secondary test of responder/nonresponder, we considered clinical response rates of 0.05 and 0.10 for the control group and .35, .40, and .45 for the treatment group. Power was greater than .95 in all cases. For comparison, we observed rates of 0.08 and 0.56 in the control and treatment groups, respectively, in [name] et al. (2011).

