The following outcomes measures will be administered to the Veteran. The primary outcome will be change in clinician-rated depression, as measured by the Hamilton Depression Rating Scale (HAM-D), which is a well-established clinician-rated instrument for depression.²⁵ Secondary clinical outcomes include responder status ¹⁵ (defined a priori as depression very much improved (1) or much improved (2) on the CGI-Improvement Scale; CGI-I), depression severity (as assessed by the Beck Depression Inventory-II, which is a well-established self-report measure of depression), ²⁶ clinician-rated anxiety (Hamilton Anxiety Rating Scale (HAMA)),²⁷ quality of life (Medical Outcome Study Short Form [SF-36]),²⁸

The Veteran will also complete a measure of Perceived Criticism.²⁹ The scale consists of ratings of perceived criticism and reactivity to criticism. The respondent completes the following two items: 1) How critical do you think you are of your family member?; 2) How critical do you think your family member is of you? For reactivity to criticism, Veterans completed the following two items: 1) When your

family member criticizes you, how upset do you get?; 2) When you criticize your family member, how upset does he/she get? For perceived criticism and reactivity to criticism, items are rated 1-10 and were summed to generate a score ranging from 1-20 with higher scores indicating greater perceived problems.

Finally, Veterans will also complete treatment Satisfaction measures,^{30,31} as well as the Working Alliance Inventory-Short Form.³² The qualitative data will be assessed with a semi-structured interview that will elicit a narrative on their experience with the treatment (see Measures). The qualitative interview will only be given to a subsample and will take place at endpoint (see Research Design and Methods, 3rd paragraph).

The following outcome measures will be administered to the Care-partner. Family Empowerment will be assessed with the 12-item family subscale from the Family Empowerment Scale.³³ Each item is rated from 1 (not at all) to 5 (very true), resulting in a sum score of 12 - 60. This measure captures the degree to which Care-partners feel they understand and respond to their Veterans' illness. Care-partners will also complete a measure of Caregiver Distress³⁴ and Perceived Criticism (same measure as Veteran).²⁹

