Unless otherwise indicated, all of the analyses below will use mixed models analysis to examine treatment effects on the specified dependent variable. There will be one between-group variable (TH-CBT versus control), one repeated measure variable (time), and group-by-time interactions (effect of interest). We will consider several correlational structures between repeated measures (e.g., compound symmetry) and determine the best structure using the Akaike's Information Criterion (AIC). Random effects will be specified for each subject. For each dependent variable, we will analyze the effect of interest (i.e., group X time) separately at each post-randomization assessment point. The models will include demographic covariates (age, sex) as indicated. Standard residual diagnostics will be applied. In the event of unaccounted-for outliers, analyses will be run with and without the outliers. Should the residuals deviate unacceptably from normality assumptions, we will use robust estimation as described and cataloged by Wilcox.³⁵

AIM 1: To evaluate the effectiveness of TH-CBT for improving Veteran outcomes in dPD. Primary Hypothesis: Depressive symptoms will decrease more for Veterans receiving TH-CBT, than for Veterans in the control group. The HAM-D is the primary depression outcome measure. Secondary Hypotheses. There will be more treatment responders in the TH-CBT group. Analyses examining depression treatment response will utilize the CGI-I (response equals CGI-I score of 1- 2).³⁶ Fisher's exact test will be used to test the hypothesis related to treatment response. A sensitivity analysis will be performed using logistic regression to examine the possible importance of covariates. Secondary Hypotheses: Secondary

outcome measures for Veterans receiving TH-CBT will show greater improvement (BDI, HAM-A, SF-36) over time than for those of Veterans in the control group. As these measures can be expected to be correlated, the significance threshold adjusting for multiple-testing will be determined by permutation-based analysis.

AIM 2: To examine the impact of TH-CBT for dPD on a variety of Care-partner outcomes. Hypotheses: TH-CBT Care-partners will feel more empowered (FES), report less distress (CDS) and be less critical (to the Veteran; PCS) relative to controls. The analysis approach will be the same as in Specific Aim 1

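### HAM-D is tested separately at four visits, and neither a visit nor an overall test is named as the one that decides the primary hypothesis

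*Combined protocol and SAP*

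**What the plan says.** Section 4.2 defines the outcome without a time point: "The primary outcome will be change in clinician-rated depression, as measured by the Hamilton Depression Rating Scale (HAM-D"). The primary hypothesis, in Sections 1.2 and 5, is a greater decrease in depressive symptoms with TH-CBT, again with no visit.

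Section 5 specifies a mixed model with group, time and "group-by-time interactions (effect of interest"), and then directs that "we will analyze the effect of interest (i.e., group X time) separately at each post-randomization assessment point". The schedule in Section 3 and Table 1 of Section 4.2 gives HAM-D four post-randomization assessments: week 5, week 10, 1 month and 6 months after treatment.

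The one rule on multiple testing comes directly after the sentence on BDI, HAM-A and SF-36: "As these measures can be expected to be correlated, the significance threshold adjusting for multiple-testing will be determined by permutation-based analysis". Its subject is those secondary measures.

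Section 3.3 speaks of one primary test of the HAM-D difference, and describes it this way: "controlling for baseline HAM-D scores and demographic covariates, the current study is powered to detect a 2.5 point HAM-D treatment difference between groups". It gives no visit, alpha, power level or numerical SD for that test.

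**The concern.** Section 3.3 assumes one primary test and Section 5 produces four. They answer different questions: early effect (week 5), effect at the end of treatment (week 10) and durability (1 and 6 months). Two readers following the plan faithfully could report different tests as primary. As far as these documents show, the choice could be made after the results are known. The error rate of the trial's one confirmatory claim is then undefined, and so is the test to which the 2.5-point power statement belongs.

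**Working it through.** **1. The plan's own figure.** The 2.5 points cannot be reproduced uniquely, because alpha, power and SD are not given. Assume two-sided alpha .05, with the 36 completing dyads per arm of Section 3.3. The implied residual SD is 2.5 / [(1.960 + z_power) × √(2/36)]:
- 80% power: 2.5 / (2.802 × 0.2357) = 3.79
- 90% power: 2.5 / (3.242 × 0.2357) = 3.27

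For comparison, take the earlier trial's difference of 7.30 (Section 3.3) and Cohen's d of 1.59 (Section 2), and assume that d is that difference divided by the SD. The SD is then 7.30/1.59 = 4.59. With residual SD 4.59 × √(1 − r²), where r is the baseline correlation, power for 2.5 points is 0.64 (r = 0), 0.76 (r = .5), 0.82 (r = .6) and 0.90 (r = .7). So the figure is plausible for one baseline-adjusted test at one time point. It does not show which time point.

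**2. Is a deciding test named anywhere?**

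| Place | What it fixes | Ties the HAM-D test to a visit or overall test? |
|---|---|---|
| Sections 1.2 and 5, primary hypothesis | HAM-D, greater decrease | No |
| Section 4.2, primary outcome | Change in HAM-D | No |
| Section 3.3, power | One test, 2.5 points | No |
| Section 5, model | Group × time, at each visit | No |
| Section 5, permutation threshold | BDI, HAM-A, SF-36 | Does not reach HAM-D |
| Section 3 and Assessments paragraph; Table 1; amendment of 7/25/18 | Week 10 called endpoint or post-treatment | Label only |

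**3. What would follow if any visit could decide.** This rule is an assumption, as is two-sided .05 per visit. Under no true effect, the four test statistics are taken as multivariate normal with cut-off 1.96. With R the within-person correlation matrix (equal variances, visit 0 = baseline), the covariance between the contrasts at visits j and k is proportional to:
- change from baseline: R_jk − R_j0 − R_k0 + 1
- baseline as covariate: R_jk − R_j0·R_k0

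Under compound symmetry with correlation r, the change contrasts correlate (1 − r)/(2 − 2r) = .5 whatever r is, and the adjusted contrasts r/(1 + r). Simulation with at least 1,500,000 draws per setting gave:

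| Assumed structure | Favouring TH-CBT (nominal 2.5%) | Either direction (nominal 5%) |
|---|---|---|
| Compound symmetry, change | 7.8% | 15.6% |
| Compound symmetry, adjusted, r .9 to .3 | 7.9% to 9.0% | 15.8% to 17.9% |
| AR(1) by visit order, .9 to .5, both contrasts | about 6.5% to 8.5% | about 13% to 17% |
| AR(1) on weeks 0, 5, 10, 14, 36, .9 to .5 per 5 weeks, both contrasts | 7.1% to 8.8% | about 14% to 17% |
| Baseline-to-post .3, post-to-post .8: change; adjusted | 5.2%; 5.9% | about 10%; 12% |
| Independent visits (upper bound) | 1 − .975⁴ = 9.6% | 1 − .95⁴ = 18.5% |

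The last correlated row matters because Section 5 leaves the structure to AIC, and post-baseline scores may agree better with each other than with baseline. Weeks 14 and 36 for the follow-ups are assumed, the first from the earlier trial's schedule.

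**4. What a single test gives.** Simulated null trials with 36 per arm, tested at week 10 alone, gave 2.45% to 2.56% favourable. An overall 4-df test of the visit contrasts gave 5.0%. After passing it, a favourable claim at any visit had probability 1.7% to 2.4% under compound symmetry and AR(1), still with no effect at any visit.

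**The case against.** The strongest reply is that week 10 is evidently meant. The Assessments paragraph calls week 5 the midpoint, week 10 the endpoint and both later visits follow-up. Section 3 selects interviewees by response at endpoint and interviews them at week 10. The amendment of 7/25/18 sets the week 10 treatment endpoint apart from the final follow-up. Section 3.3 also benchmarks response against the earlier trial, where "we observed rates of 0.08 and 0.56 in the control and treatment groups, respectively"; Section 2 shows that these are week 10 figures: "At week 10, 56% patients receiving CBT and 8% receiving standard care were treatment responders". This stands as evidence of intent and narrows the choice. But the labels describe a schedule, and the benchmark concerns the secondary responder comparison. None is attached to the HAM-D test, while Section 5 treats all four visits alike.

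A second reply is that group × time is itself an overall test, as the single HAM-D F test with 3 numerator df in Section 2 suggests for the earlier trial. Yet Section 5 directs that this same effect be analysed visit by visit, and states no joint test or gate.

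A reader might also infer that the plan inflates its primary error rate. The documents do not support that: they never say that one significant visit confirms the hypothesis, and under either reading above the rate is nominal. Nor do they support the inference that HAM-D will be compared by arm during the trial. Section 6 lists interim analyses among the contents of annual IRB reports, without specifying a by-arm comparison. That is only a reason to settle the choice early.

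**Conclusion.** The gap is real and should be closed before outcome data are seen by arm: four HAM-D tests are planned, one primary test is powered, no multiplicity control reaches HAM-D, and nothing connects the powered test to one of the four or to an overall test. This rests on the text alone. The illustrative size is about 5% to 9% false claims for TH-CBT against 2.5%, or about 10% to 18% in either direction against 5%. It depends on an assumed alpha, assumed correlations and an any-visit rule that the plan does not contain. It shows what the missing sentence protects against, not the plan's actual error rate.

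**What to change.** Before outcome data are seen by arm:
- **Section 4.2:** state that the primary outcome is change in HAM-D from baseline to week 10.
- **Section 5:** state that the primary test is the between-group HAM-D contrast at week 10 from the mixed model, at two-sided alpha .05, and that the other HAM-D visits are secondary. Say once whether baseline HAM-D is a covariate, as in Section 3.3, or a repeated outcome, as Section 5 implies with age and sex as its only named covariates. The two sections must agree.
- **Section 3.3:** tie the 2.5-point statement to this test, with its alpha and power.

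A pre-stated overall group × time test, passed before any visit is interpreted, is an acceptable alternative. The 2.5-point statement would then need recalculating. If baseline becomes a covariate, the overall test must cover the group differences at all four visits, because the interaction alone would miss a benefit that is constant over time.

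Keeping all four visits able to decide costs more. Bonferroni at .05/4 = .0125 lowers 80% power at a given visit to 62%, and raises the detectable difference by (2.498 + 0.842)/(1.960 + 0.842) = 1.19, from 2.5 to about 2.98 points.

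The recommended change costs a few sentences and one modelling decision, with no change to visits, measures or sample size. Its downside is that a benefit seen only at another visit becomes a secondary finding.

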17: $F(3,56)=18.50, P<.0001$; Cohen's $d=1.21$ and BDI: $F(3,53)=23.68, P<.0001$]. This trial demonstrated that the same treatment can be delivered remotely with a similar level of treatment impact.

Combined, these initial studies provide support for the CBT package and for its remote delivery (i.e., telehealth). The current trial therefore proposed to test the delivery of this treatment via video-to-home telehealth. This modality of care has been rolled out by the VHA and therefore provides an existing infrastructure to make this intervention available to Veterans with dPD, who face access barriers to treatment. For example, at VA New Jersey, 583 mental health encounters have been conducted via video-to-home telehealth in FY14.

3. Research Design and Methods

Participants will include 90 Veterans (ages 35-85) with dPD and their Care-partners (N=180 total: 90 Veterans with PD and 90 Care-partners). Since Care-partners will be designated by their Veteran with PD, they will not likely be Veterans themselves. The justification for including nonveterans is due to the fact that Care-partners serve as an integral part of the treatment team for Veterans with dPD. Thus, we are evaluating the clinical effectiveness of an intervention that involves Care-partners in order to optimize Veteran depression treatment response and Care-partner well-being.

The clinical effectiveness of a 10-session telehealth-based cognitive-behavioral treatment package (TH-CBT) for dPD will be evaluated. Study conditions are as follows:

- [Intervention] Half of the Veterans will receive telehealth-based CBT, in addition to their standard care (i.e., treatment-as-usual under the care of their personal physicians).
- [Control] The other half will receive their standard care only during the study period. Participants will be randomly assigned to treatment group via computer generated random assignment. Randomization will be stratified by antidepressant use at baseline (yes/no).

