3.4.1 Inclusion Criteria

Veteran Inclusion Criteria:

- 1) Confirmed PD diagnosis in the VA medical record;
- 2) Primary Major Depression, Dysthymia, or Depression NOS of at least moderate severity per the SCID;⁸⁷
- 3) Access to a computer/tablet with high-speed internet access. Comorbid anxiety disorders are not exclusionary if the depressive disorder is primary.
- 4) Ages 35-85;
- 5) Stable medication and mental health regimen (including applicable antidepressants, other psychotropic agents, movement disorder drugs, clinic-based psychotherapies) \geq 6 weeks). This means that the medication regimen and treatment plan have been consistent for at least 6 weeks.
- 6) Family member or friend willing to participate;

Veteran Exclusion Criteria:

- 1) Possible dementia or marked cognitive impairment [Montreal Cognitive Assessment Score (MoCA) $<$ 21].¹⁷
- 2) Motor fluctuations \geq 50% of the day;
- 3) Acute suicidal plans or intent (determined by clinical interview);
- 4) Unstable medical conditions;
- 5) Bipolar, Psychotic Spectrum, or Substance Use Disorders.

Exclusion Criterion 1 above is due to dementia being associated with numerous clinical variables (e.g., motor fluctuations, delusions) that make the rating of depression difficult. Dementia may also compromise the clinical effectiveness of a non-pharmacological treatment due to its impact on cognitive processes. As dementia is not typically seen in the early stages of PD, results from the current study should generalize to the larger PD population without dementia.

Care-partner Inclusion Criteria:

- 1) Ages 25-85;
- 2) Daily contact with Veteran

Care-partner Exclusion Criteria:

- 1) Unstable medical/psychiatric conditions (clinical interview).

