Baseline Assessment: After the screening and consent, appropriate individuals will be scheduled for a telephone appointment. Demographic information will be obtained, and inclusion/exclusion criteria will

be assessed. A detailed medical (i.e., number of medical conditions, duration and stage of PD) and psychiatric history (i.e., number past depressive episodes, past treatments), and a current list of all prescription and over-the-counter medications will be gathered. Clinician-administered rating scales and self-report measures will be completed. The screening appointment typically lasts between 2 and 3 hours. If participants are unable to complete the entire screening evaluation in one day, a second telephone appointment will be scheduled within the next 7 days to complete the remainder of the screening procedures.

Randomization: All appropriate candidates will be randomly assigned to receive either: 1) telehealth-based cognitive-behavioral therapy plus standard care (the “intervention”) or 2) standard care, based on computer generated random assignment, after the screening appointment (the “control group” treatment). Randomization will be stratified by antidepressant medication (ADM) use at baseline (yes or no) such that patients taking ADMs are equally represented in both treatment conditions. Patients will be notified of their assignment to group via telephone in the week following their baseline assessment.

Assessments: Participants will be assessed at baseline (week 0), midpoint (week 5), endpoint (week 10), and follow-up (1 and 6 months post-treatment). Follow-up assessments will be conducted via telephone for the clinician-rated instruments (i.e., HAM-D, HAM-A). Self-report questionnaires will be mailed to participants with a self-addressed envelope that can be returned to the research team upon completion. If participants request assistance with the self-report questionnaires, they will be mailed to them and also read aloud to them by telephone. These assessments will last 1-2 hours.

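### Randomization is stratified by baseline antidepressant use, but the Veteran outcome models do not name it; adding it with its time interaction is a free, low-priority gain of about 0 to 3 points of power.

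*Combined protocol and SAP*

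**What the plan says.** Section 3 gives the design: "Randomization will be stratified by antidepressant use at baseline (yes/no"). The Randomization paragraph under Section 3.4.3 repeats it and gives the purpose, "such that patients taking ADMs are equally represented in both treatment conditions". No other stratification factor is listed.

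Section 5 sets out mixed models with group, time and group-by-time, the last tested at each post-randomization visit. On covariates it says: "The models will include demographic covariates (age, sex) as indicated". Section 3.3 describes the primary HAM-D test as "controlling for baseline HAM-D scores and demographic covariates" and says the trial is "powered to detect a 2.5 point HAM-D treatment difference between groups", with 36 completing dyads per arm.

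Three other places touch the subject without settling it:

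- Section 3.5 allows for possible control of standard-care covariates. This is optional, tied to no model, and concerns care received during the study.
- The logistic sensitivity analysis of response in Section 5 names no covariates.
- The permutation-based multiplicity adjustment in Section 5 does not say whether labels are permuted within strata.

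None of the listed amendments adds the stratum.

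**The concern.** Stratified allocation takes the between-arm variation due to the stratum out of the treatment estimate. A model that omits the stratum leaves its contribution in the error variance. If antidepressant use predicts change in HAM-D, the standard error is then too large, the test somewhat conservative, and power is given away. Permuting labels across strata has the same effect on the multiplicity adjustment.

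Antidepressant use is not a demographic variable, so neither covariate statement covers it. The qualifier that ends the Section 5 sentence also leaves the covariate set to be decided later; naming the stratum in advance removes one such choice.

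**Working it through.** **Planned detectable difference.** The 2.5 points cannot be reproduced, because SD, alpha and power are not stated. With 36 per arm and two-sided .05, the implied residual SD is 2.5 / [(1.960 + 0.842) × √(2/36)] = 3.8 at 80% power, or 3.3 at 90% (1.282 in place of 0.842).

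**Assumptions, none in the documents.** 18 users and 18 non-users per arm, within-stratum SD 1, correlation .5 between visits, and a stratum effect *e* on change from week 5 onward. Treatment effects were set for power near .80: .67 SD for the joint and change tests, .585 SD for the baseline-adjusted test.

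**By hand, change from baseline to week 10, e = .5.**

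- Variance of change within strata: 2(1 − .5) = 1. Sampling SE of the treatment contrast: √(2/36) = .2357.
- With half in each stratum, omission adds e²/4 = .0625 to the error variance, so the reported SE is too large by √1.0625 = 1.031.
- Noncentrality: .67/.2357 = 2.84. Raising the critical value of t (70 df) by 1.031 gives power .783, against .800 with the stratum. Type I error becomes about .044.

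**Simulation, 60,000 trials per setting, power without v with the stratum (with stratum-by-time in the joint model).**

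| *e* (SD) | Joint five-visit model | Change contrast | Baseline-adjusted |
|---|---|---|---|
| .3 | .806 v .808 | .795 v .801 | .793 v .802 |
| .5 | .799 v .806 | .780 v .798 | .781 v .804 |
| .8 | .791 v .808 | .753 v .801 | .739 v .803 |
| 1.0 | .781 v .808 | .729 v .800 | .703 v .800 |

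In the last two rows antidepressant use predicts change more strongly than treatment does, so they are extremes. Two independent reruns of 20,000 trials per setting, at .5 and 1.0 SD, agreed within simulation error.

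**At the planned 2.5 points.** In the previous trial, "we observed a group difference of 7.30", and Section 2 gives d = 1.59 for HAM-D. If the two share one SD (an assumption), it is 7.30/1.59 = 4.59, and 2.5 points is .54 SD. For *e* = .3 and .5 the powers are: joint .628 v .632 and .625 v .634; change .614 v .622 and .602 v .626; baseline-adjusted .731 v .740 and .714 v .742. At *e* = .8 and 1.0 the joint model loses 2.4 and 3.7 points.

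**Larger treatment effects.** At 1.0 SD the loss is at most 0.3 (joint), 1.1 (change) and 0.4 points (baseline-adjusted), even with *e* = 1.0. At 1.59 SD it is nil.

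**A user v non-user difference constant over time.** At .5 and .8 SD the loss is 0 in group-by-time, and 0.5 and 1.4 points in the baseline-adjusted test.

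**Type I error without the stratum** (*e* = .3, .5, .8, 1.0; 20,000 trials each):

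- Exact balance: joint .048, .048, .043, .041; change .046, .044, .036, .030; baseline-adjusted .046, .042, .031, .024.
- Simple allocation inside strata: the single-visit tests stay between .048 and .051. A random-intercept model rises to .052, .055, .059, .065, because the omitted stratum-by-time effect breaks compound symmetry. The plan's choice of structure by AIC may reduce this.
- With the stratum, all lie between .047 and .054.

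**Main effect or interaction.** REML SE of group-by-time at week 10 (90 subjects, 20% dropout, *e* = .5): .2219 with no stratum, .2219 with the main effect, .2191 with stratum-by-time added.

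**Permutation** (BDI-II, HAM-A, SF-36 correlated .5; effect .67 SD; 6,000 trials). Mean power per outcome, across v within strata: .679 v .680 if not prognostic, .657 v .667 at .3 SD, .639 v .664 at .5 SD. Family-wise error at .5 SD is .039 across and .047 within.

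**The case against.** The case against acting is that this is a refinement and not a defect. Balance of antidepressant users between arms is delivered by the design, and validity does not depend on the covariate. The joint-model gain is under 1 point unless antidepressant use is very strongly prognostic; figures near 3 need effects larger than the treatment effect itself. The pattern required is also uncertain. Eligibility demands that "the medication regimen and treatment plan have been consistent for at least 6 weeks", and Section 4.1 keeps existing treatments in place, so a difference constant over time is at least as plausible, and that costs nothing in group-by-time. Prevalence, prognostic strength, SD and correlation are all assumed. Section 3.5 shows that medication adjustment was contemplated, and on permutation the plan is silent and not wrong.

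Most of this stands, and it fixes the priority as low. It does not remove the point. Section 3.5 commits no model to the baseline stratum, and silence on the permutation scheme leaves the choice open. The objection that a main effect gains nothing for group-by-time is correct, and is why the interaction must be specified.

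**Conclusion.** The concern holds, at low priority. The only stratification factor is absent from the named covariates of the Veteran models and of the baseline-adjusted primary comparison. Under balance within strata the results remain valid and type I error is not inflated.

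The cost in the planned joint model is about 0 to 3 points of power at a base near .80: under 1 point for a stratum effect on change up to .5 SD, and 2.7 at 1.0 SD. The one joint-model figure above that range is 3.7 points, for a 1.0 SD stratum effect at the planned 2.5-point difference. The single-visit tests lose more for the same stratum effect: 1.8 points (change) and 2.3 (baseline-adjusted) at .5 SD. The loss is nil if antidepressant use is not prognostic or if the treatment effect is near that of the previous trial. The omission follows directly from the documents; the sizes rest on the assumptions listed, so confidence in them is moderate.

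**What to change.** 1. In the Veteran mixed models (HAM-D, BDI-II, HAM-A, SF-36), prespecify baseline antidepressant use and its interaction with time as fixed effects, whatever is decided about age and sex.
2. If the baseline-adjusted comparison in Section 3.3 is the primary test, add the stratum there as a covariate.
3. State that treatment labels are permuted within antidepressant strata in the multiplicity procedure.
4. Name the stratum among the covariates of the logistic sensitivity analysis of response.

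Fisher's exact test can stay, and the Care-partner models need not include the stratum.

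The cost is SAP wording and five degrees of freedom in each five-visit model (one for the stratum, four for its interaction with the post-baseline visits). With no stratum effect, simulated power changed by no more than 0.1 point. The variable is already recorded at randomization.
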